9.7.1.15 Safety Analyses

All safety analyses will be performed on the safety analysis set.

The change in INR and aPTT from baseline at 1 hour after study drug administration will be compared using descriptive statistics for the various treatment groups.

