On the day of study drug administration (V1a), subjects will be randomized (2:1:2:1); URG101:placebo:lidocaine:heparin) and will receive a single administration of one of four intravesical treatments in a blinded fashion, based on random assignment:

1. Combination product, URG101 (buffered heparin-lidocaine)
2. Placebo: [REDACTED]
3. Lidocaine: [REDACTED]
4. Heparin: [REDACTED]

Subjects will be monitored for 2 hours in the clinic after study drug administration.

CLINICAL PROTOCOL SYNOPSIS (continued)

	
Subjects will maintain a urination log and symptom diary after discharge and will return to the clinic the following day to complete the in-clinic study procedures and collection of the study diary.
 
The following will be completed according to the schedule of assessments over a 24-hour period after study drug administration: the 11-point NRS for bladder pain and urgency; the PORIS questionnaire; vital signs assessments; blood samples for safety laboratory assessments, i.e. blood coagulation (prothrombin time [INR] and activated partial thromboplastin time [aPTT]), and plasma lidocaine concentrations; adverse events; and concomitant medication assessments.
 
Subjects will be contacted within 48 to 72 hours after the last study treatment to follow-up on any ongoing adverse events after the last clinic visit.
 
The clinical study will plan to randomize 180 subjects. After 90 (50%) subjects have been enrolled and treated, the IDMC will examine the conditional power and determine if a modification to the sample size is required to yield an overall power of 90%. An adjustment to the type 1 error rate will not be necessary if the conditional power is >39% at the interim assessment.
 
The IDMC will consist of 3 members: 1 physician expert in IC/BPS, 1 expert in clinical development, and a biostatistician. None of the IDMC members will be associated with study personnel; all communication between the IDMC and study personnel will be pre-defined and governed by the IDMC charter. The IDMC will have access to unblinded pain scores to perform their ranking of the pain endpoints and for assessment of conditional power.

Estimated Number of Subjects:	A target of 180 subjects subject to adjustment by the IDMC. A maximum of 300 subjects will be enrolled in Study URG101-105.
Number of Study Sites:	Up to 30 sites in the United States and Canada

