Statistical Methods:	
Sample Size Estimate Sample size estimates were based on a pilot trial of heparin-lidocaine versus lidocaine alone and a prior two-arm study of URG101 versus placebo. The primary efficacy endpoint is SPID-12. The sample size calculation is based on a one-way analysis of variance, comparing SPID-12 from four treatment groups. A target sample size of 180 subjects to be allocated unequally among the four treatment groups as follows: URG101:placebo:lidocaine: heparin at 2:1:2:1 (60 subjects per group and 30 subjects per group). This sample size is sufficient to achieve 90% power to detect a difference between the URG101 and lidocaine groups assuming a treatment effect size of 0.60. The study will also have 90% power to detect a difference between the URG101 and each of the placebo and heparin groups assuming an effect size for these comparisons of 0.75. Once 90 subjects have been enrolled, a blinded interim analysis will take place; and, if required, the number of subjects for the study increased to a maximum of 300 subjects.
 
Description of Analysis Sets: All analyses of the efficacy of URG101 will be performed on the ITT set, which will include all randomized subjects from the investigative phase of the study who receive study drug. These efficacy analyses will compare the treatment groups on the basis of randomized treatment, regardless of the treatment actually received. Primary efficacy and key secondary efficacy analyses will also be conducted on a per protocol set, which will include all subjects in the ITT set who sufficiently comply with the protocol.
 
Safety analyses will be based on the safety analysis set which will include all subjects who receive at least one dose of study drug and have at least one post dose safety assessment in both phases of the study. Safety summaries will be produced based on study treatment actually received.

CLINICAL PROTOCOL SYNOPSIS (continued)

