	
Primary Efficacy Determination: The primary efficacy endpoint will be compared between the URG101 and the lidocaine, heparin, and placebo groups using an analysis of covariance model which will include factors for treatment and baseline pain values. Pairwise comparisons of least squares means between URG101 and each of the other treatment arms will be performed. If the p-value associated with these comparisons is < 0.05 in favor of URG101, the primary aim of the trial will be confirmed.
 
Missing data for efficacy values will be imputed by the last observation carried forward method.
 
Secondary Efficacy Determinations: Analyses of secondary endpoints relating to changes in the NRSs for pain and urgency will be performed using analysis of covariance models similar to that used for the primary efficacy endpoint. Nonparametric methodology in exploratory analyses may be used to supplement the parametric analyses.
 
Treatment group comparisons relative to improvement on the PORIS questionnaire, (Question 3), will be made with standard contingency table techniques.
 
Pharmacokinetic Determinations: A comparison of pain and urgency assessments as measured by 11-point NRS to plasma lidocaine concentrations at 1 hour after study drug administration will be made for the PK set.

	
Safety Determinations: All safety analyses will be performed on the safety analysis set.
 
The change in INR and aPTT at baseline and 1 hour will be compared for the various treatment groups using descriptive statistics.
 
Other Determinations: Demographic and disposition data, randomization, drug administration, medical history, prior and concomitant medications, adverse events, clinical laboratory measurements, vital signs, physical examination findings, and all other safety data will be listed by subject and time point. Descriptive statistics will be tabulated for change from baseline in the vital signs. In addition to clinical and laboratory assessments, subject safety will be monitored by recording adverse events and serious adverse events throughout the study. Any pregnancy that occurs during the study will be promptly reported to the sponsor, but will not be considered a serious adverse event. Treatment-emergent adverse events will be summarized by type, frequency, severity, relationship to study drug, and number of subjects per treatment. Adverse events will be coded according to the Medical Dictionary for Regulatory Activities.

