7.3 CLINICAL EXPERIENCE WITH URG101

Previously, URG101 was studied in open-label clinical studies at the University of California – San Diego¹³ and in a controlled Phase 2 multicenter trial sponsored by Urigen. These studies demonstrated that URG101 was safe and well tolerated. No serious adverse events (SAEs) or unexpected adverse events (AEs) or significant changes in blood coagulation were observed, demonstrating that heparin in the bladder does not appreciably enter into systemic circulation.

In the URG101-104 study, a multicenter, single-dose, cross-over, double-blind, placebo-controlled study, followed by one open label treatment, a total of 28 subjects were enrolled²⁰. The study was terminated early due to a recall of heparin with no suitable replacement, and the planned interim analysis became the final unblinded analysis. Statistical significance was achieved for the primary endpoint (i.e., average percentage change in pain from 0.5 to 12 hours), was 42% on URG101 compared with 21% on placebo ($p = 0.03$). Similar results were seen with the secondary endpoints of $\geq 50\%$ overall improvement ($p = 0.01$) and average percentage change in pain plus urge and urge alone ($p = 0.03$).

7.4

RISKS AND BENEFITS

The study drug components (Lidocaine Hydrochloride and Heparin Sodium) both have extensive previous human experience since their United States approvals in 1948 and 1939, respectively. Additionally, both of these drugs are normally administered via parenteral injection, whereas intravesical alkalinized lidocaine-heparin is administered into the lumen of the bladder and only comes into contact with the urothelium.

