9.7.1.3 Safety Endpoints

The safety endpoints of the study are:

1. Change from baseline in INR at 1 hour after study drug administration.
2. Change from baseline in aPTT at 1 hour after study drug administration.
3. Adverse events

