9.7.1.12 Laboratory Values

Summary statistics for changes from baseline and the incidence of treatment emergent abnormal values in coagulation measurements at 1 hour post drug administration will be provided.

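### INR and aPTT, the first two safety endpoints, get only per-arm descriptive summaries, so the plan does not state how large a heparin effect on coagulation has been excluded; a baseline-adjusted heparin v no-heparin estimate with an interval would be a cheap addition

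*Combined protocol and SAP*

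**What the plan says.** Section 9.7.1.3 and the synopsis name three safety endpoints. The first two are "Change from baseline in INR at 1 hour after study drug administration" and "Change from baseline in aPTT at 1 hour after study drug administration"; the third is adverse events. Section 9.1.2 schedules both coagulation tests before dosing and at 1 hour, with no distinction by arm.

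The planned analysis is the same wherever it appears:

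- Section 9.7.1.15: the changes "will be compared using descriptive statistics for the various treatment groups".
- Synopsis, safety determinations: "The change in INR and aPTT at baseline and 1 hour will be compared for the various treatment groups using descriptive statistics".
- Section 9.7.1.12: "Summary statistics for changes from baseline and the incidence of treatment emergent abnormal values in coagulation measurements".
- Section 9.7.1.9: all safety data are summarised by treatment group, as treated, with n, mean, SD, median and range, or counts and percentages.

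No section gives a difference between arms, a confidence interval, an adjustment for the baseline value or a heparin v no-heparin contrast for INR or aPTT. Sections 9.7 and 9.7.1 leave further detail to a separate SAP, whose text is not part of the document reviewed.

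On the background evidence, Section 7.3 describes earlier coagulation results as "demonstrating that heparin in the bladder does not appreciably enter into systemic circulation". Sections 7.4 and 7.5.1 argue along the same lines.

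**The concern.** The coagulation endpoints serve a claim of absence: that heparin placed in the bladder does not reach the circulation to any extent that matters. Such a claim is supported by showing how large an effect the data exclude. Arm means and SDs, read one beside another, do not state that.

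Earlier evidence at the proposed dose is limited. Section 7.5.1 reports 28 subjects, with 51 exposures, at 50,000 units. The present trial has randomised heparin-free arms and a baseline value for each test, so it can give the bound from data it already collects. The method is also already in the plan: Section 9.7.1.14 uses baseline-adjusted ANCOVA with contrasts for efficacy.

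Section 9.5.1.10.1 sends coagulation tests to local laboratories, and there may be 30 sites. An arm of 30 would then average one subject per site (30/30), a further reason to prefer a baseline-adjusted comparison to inspection of arm means.

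**Working it through.** **Inputs.** The synopsis gives "A target of 180 subjects subject to adjustment by the IDMC", with a maximum of 300, allocated "URG101:placebo:lidocaine: heparin at 2:1:2:1 (60 subjects per group and 30 subjects per group"). So URG101 = 60, placebo = 30, lidocaine = 60, heparin = 30. Section 9.7.1 sets two-sided alpha at 0.05. No SD, margin or precision target is given for INR or aPTT, so precision is expressed in SDs of change.

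**Step 1. Reproduce the plan's own figure.** The only stated figure is 90% power for SPID-12. Power = Φ(d/SE − 1.96), with SE = √(1/n₁ + 1/n₂).

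- URG101 v lidocaine, d = 0.60: SE = √(2/60) = 0.1826; 0.60/0.1826 − 1.96 = 1.33; power 90.8% (90.3% by noncentral t).
- URG101 v placebo or heparin, d = 0.75: SE = √(1/60 + 1/30) = 0.2236; 0.75/0.2236 − 1.96 = 1.39; power 91.8% (91.3% by noncentral t).

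Both agree with the stated 90%, so the arm sizes are read correctly.

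**Step 2. Precision of the heparin effect.** With heparin: 60 + 30 = 90. Without: 60 + 30 = 90. Half-width = 1.96 × SE.

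| Contrast | n | Variance (SD²) | SE | 95% half-width |
|---|---|---|---|---|
| Heparin v placebo | 30 v 30 | 0.0667 | 0.258 | 0.51 |
| URG101 v lidocaine | 60 v 60 | 0.0333 | 0.183 | 0.36 |
| Heparin v no heparin | 90 v 90 | 0.0222 | 0.149 | 0.29 |

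Variance ratios against the pooled contrast are 0.0667/0.0222 = 3.0 and 0.0333/0.0222 = 1.5. Interval width goes with the square root: √3.0 = 1.73 and √1.5 = 1.22.

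Each pool holds 60 subjects with lidocaine and 30 without, or the reverse by arm: 60 of the 90 in each pool received lidocaine. Lidocaine is therefore balanced, and stratifying by it leaves the variance at 0.0222. An equal-weight factorial main effect has variance 0.25 × (1/60 + 1/30 + 1/60 + 1/30) = 0.025, half-width 0.31.

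At 300 subjects (100/50/100/50) the three half-widths become 0.39, 0.28 and 0.23; the ratios do not change.

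**Step 3. Interaction check.** Variance = 1/60 + 1/30 + 1/60 + 1/30 = 0.1; SE = 0.316; half-width = 0.62 SD. A moderate interaction could go unseen.

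**Step 4. No abnormal value observed.** Two-sided exact 95% upper limit = 1 − 0.025^(1/n): 11.6% for n = 30, 6.0% for n = 60, 4.0% for n = 90. One-sided 95% limits, 1 − 0.05^(1/n), are 9.5%, 4.9% and 3.3%; these do not correspond to a two-sided 95% interval.

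**The case against.** Descriptive safety reporting is a legitimate choice in a phase 2a trial. The plan applies one rule to all safety data, does not contradict itself, and promises no test or bound for INR or aPTT. Three further points stand:

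- Section 9.7.1.9 calls for n, mean and SD by arm. From these a reader could compute the unadjusted 90 v 90 difference and its interval, and exact limits follow from the incidence counts. What the plan lacks is a prespecified, baseline-adjusted estimate. How much the adjustment would narrow the interval cannot be stated from the documents.
- The safety objective concerns URG101 itself, so a pooled estimate must not displace the data from its 60 subjects. A pooled mean is also insensitive if only a few subjects absorb heparin; the abnormal-value incidence and the by-subject listings address that case.
- Pooling needs comparable heparin exposure in both heparin arms. Section 7.5.1 gives 50,000 units for URG101. Section 9.4.1 describes 12 mL of heparin in the heparin arm, which at the 5,000 USPU/mL named in the objectives is nominally 12 × 5,000 = 60,000 units. Redacted strengths and instillation steps may reconcile these, but the documents do not let us check.

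Two stronger readings are tempting. A reader might infer that pooling makes the interval three times narrower. It does not: 3.0 is a variance ratio, and only against the smallest contrast. URG101 v lidocaine already isolates heparin at 60 v 60, and against it the gain in width is 1.22. A reader might also infer that the planned analysis is wrong. Nothing in the documents supports that, since no inference is drawn from the summaries.

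The separate SAP might add an interval. That cannot be assumed, because Section 9.7.1.15 itself commits to descriptive statistics.

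**Conclusion.** The point holds as a worthwhile, inexpensive improvement. As written, the plan reports the two coagulation endpoints without stating how large a heparin effect has been excluded, although the safety case depends on that. A pooled heparin effect would have a planned 95% half-width of 0.29 SD, against 0.36 SD for URG101 v lidocaine and 0.51 SD for heparin v placebo. The gain over the better of the two existing contrasts is modest; the larger gain is having any stated estimate and interval at all.

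This rests on the planned numbers and a common SD. Actual safety-set numbers may be smaller, or larger if enrolment rises towards 300. It also rests on lidocaine not modifying heparin's effect, which the interaction display can check only roughly, and on comparable heparin exposure in the two heparin arms, which is unverified. Without an SD or clinical margin in the documents, none of these half-widths can be called reassuring or otherwise.

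**What to change.** In Section 9.7.1.15, with a matching line in the synopsis, keep the per-arm summaries and add:

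1. An ANCOVA of the 1-hour change in aPTT, and likewise in INR, with heparin (yes/no), lidocaine (yes/no) and the baseline value. Report the heparin effect with a 95% CI, as estimation only, with no test.
2. Beside it, URG101 v lidocaine and heparin v placebo, each with a 95% CI, and the heparin-by-lidocaine interaction with its interval, presented as a display and not as proof of no interaction.
3. The incidence of treatment-emergent abnormal values per arm, and for the pooled heparin-containing and heparin-free arms, with exact two-sided 95% CIs.

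Before pooling, the sponsor should confirm that heparin exposure is comparable in the URG101 and heparin arms and reconcile the stated volumes and units. If it is not comparable, the report should rely on the two within-stratum contrasts.

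The cost is one model per endpoint and one table. No new data are needed and, since nothing is tested, no alpha is spent. The downside is reliance on the two pooling assumptions, which showing the within-stratum contrasts keeps in view.

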9.7.1.16 Pharmacokinetic Analyses

Samples collected at baseline will be analyzed to determine if plasma lidocaine concentrations are detected prior to study drug administration. A comparison of peak pain and urgency as measured by 11-point NRSs to plasma lidocaine levels at 1 hour after study drug administration will be made for the PK set.

9.7.2 Handling of Missing Data

9.7.2.1 11-Point Bladder Pain and Urgency Scales

For the 11-point numerical data, if subjects are administered any rescue pain medication, the pain score recorded immediately prior to receiving the rescue pain medication will be carried forward for 4 hours. Data for subjects who withdraw will be imputed using the baseline observation carried forward method. The imputed dataset will be used to derive the SPID score.

9.7.2.2 24-Hour Symptom and Urination Diaries

During the 24 hours after treatment, subjects are required to fill in their symptom diaries only while they are awake. Missing data occurring will be imputed using LOCF methodology.

[figure not shown]
If the number of missing data points in the 12-hour period after treatment administration is 6 or greater, then the subject is considered a major protocol violator and his or her data are excluded from the per protocol analysis. If the number of missing data points in the first 6-hour period following treatment administration is 3 or greater, then the subject is considered a major protocol violator and the subject's data are excluded from the per protocol analysis.

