9.5.7 Completion and Discontinuation of Subjects

A subject may elect to discontinue the study at any time for any reason without prejudice. All subjects who discontinue the study are to complete the study's Visit 2 procedures and the follow-up phone call indicated in the schedule of assessments ([Table 4](#)) whenever possible.

The investigator will promptly explain to the subject involved that the study will be discontinued for that subject and provide appropriate medical treatment and other necessary measures for the subject. A subject who has ceased to return for visits will be followed up by mail, phone, or other means to gather information such as the reason for failure to return, the status of treatment compliance, the presence or absence of AEs, and clinical courses of signs and symptoms. This information will be recorded in the CRF.

Subjects who discontinue early from the study will be discontinued for one of these primary reasons: AE(s), lost to follow-up, catheter intolerance, inadequate therapeutic effect, withdrawal of consent, pregnancy, study terminated, or other (to be specified). In addition to the primary reason, the subject may indicate one or more secondary reasons for discontinuation.

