9.7.1.14 Efficacy Analyses

All SPID endpoints will be calculated using Simpson's trapezoidal rule. SPID will be calculated as follows, where n is the total number of time points within the time period with non-missing imputed PID values:

If multiple scores are recorded at the same date and time, the most conservative PI scores (highest) will be used.

Primary Efficacy Analyses

The primary efficacy analyses will be performed on the intent-to-treat set. As a sensitivity analysis, the primary efficacy analysis will also be performed on the PP set. Primary efficacy analyses will also be conducted on the per protocol set, which will include all subjects in the ITT set who sufficiently comply with the protocol.

The primary efficacy endpoint will be compared between the URG101 group and the lidocaine, heparin, and placebo groups using an analysis of covariance model including factors for site and randomized treatment assignment; baseline pain will be added to the model as a covariate. Pairwise comparisons of least squares means between URG 101 and the two active treatment arms, as well as the placebo arm, will be performed. The probability values will be derived using the contrast statement from the model. If the p-value associated with these comparisons is < 0.05 in favor of URG101, the primary aim of the trial will be confirmed.

Sites with small numbers of patients enrolled may be pooled for analysis. The method used to determine pooling will be specified in the statistical analysis plan and any pooling will be finalized and documented prior to database lock and unblinding.

Secondary Efficacy Analyses

Analyses of the secondary endpoints relating to changes in the pain and urgency NRS will be performed using analysis of covariance models similar to those used for the primary efficacy endpoint. The ITT set will be used. Nonparametric methodology in exploratory analyses may be used to supplement the parametric analyses.

Treatment differences based on the PORIS questionnaire, Question 3, will be analyzed by pairwise Cochran-Mantel-Haenszel Tests based on $\geq 50\%$ improvement of symptoms.

Time to first pain medication use will be analyzed using Kaplan-Meier methodolgy. Log-rank tests will be used to compare the treament groups.

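### The synopsis and section 9.7.2.1 give different imputation rules for subjects who withdraw (LOCF and BOCF), and each rule flatters SPID-12 for one kind of withdrawal

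*Combined protocol and SAP*

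**What the plan says.** Section 9.7.2.1 sets the rule for the pain and urgency scales: "Data for subjects who withdraw will be imputed using the baseline observation carried forward method". It continues: "The imputed dataset will be used to derive the SPID score". It makes no exception for a subject whose last score is above baseline.

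The synopsis, under the primary efficacy determination, gives another rule: "Missing data for efficacy values will be imputed by the last observation carried forward method". It does not separate withdrawals from other gaps.

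Section 9.7.2.2 covers the home diary, which holds the scores from 4 hours on: "Missing data occurring will be imputed using LOCF methodology". It does not say whether this stops at withdrawal.

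Rescue has its own rule in 9.7.2.1: "the pain score recorded immediately prior to receiving the rescue pain medication will be carried forward for 4 hours".

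Section 9.7.1.14 computes SPID from the imputed differences and analyses the primary endpoint in the ITT set. The only sensitivity analysis that it names for that endpoint is the per protocol set.

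**The concern.** Two rules apply to the same missing scores of the primary endpoint, and they can give very different values. Each also has a one-sided weakness.

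- **BOCF** is cautious for a subject who leaves while better than baseline. For one who leaves while worse, it lowers every later score to baseline, and SPID-12 becomes less negative than if the last score had been kept.
- **LOCF** keeps the raised pain of the second subject, but it also carries the improvement of the first through to 12 hours.

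The rescue rule shows the contrast within one paragraph. A subject with raised pain who takes rescue keeps that pain for 4 hours, while a subject with the same pain who withdraws returns to baseline at once.

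At stake is the mean SPID-12 of whichever arm holds such subjects. In a control arm, BOCF for worsened subjects understates the benefit of URG101. In the URG101 arm it overstates it.

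**Working it through.** **Reference figures.** The plan gives no figure for the effect of its imputation rule. Its power figures do reproduce. With noncentrality d × √(n1·n2/(n1+n2)) and two-sided alpha 0.05:

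- 60 v 60 at 0.60: 0.60 × √30 = 3.29, power 90.8% (noncentral t: 90.3%).
- 60 v 30 at 0.75: 0.75 × √20 = 3.35, power 91.8% (noncentral t: 91.3%).

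Both agree with the stated 90%. They serve below only as a scale.

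**Inputs.** Assessment times are 0, 0.5, 1, 2, 4, 6, 8, 10 and 12 h (9.5.2.3). Entry pain is at least 5 on a 0 to 10 scale (9.3.1), so pain can rise by at most 5 points. Arm sizes are 60, 30, 60 and 30 (synopsis). The SPID formula is not legible in the available text. I assume PID = baseline minus current score, and the plain trapezoid.

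**A subject who worsens.** Baseline 6, scores 7, 8 and 9 at 0.5, 1 and 2 h, then withdrawal. PIDs are 0, -1, -2, -3.

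- 0 to 2 h: -0.25 - 0.75 - 2.5 = -3.5.
- BOCF, 2 to 4 h: 2 × (-3 + 0)/2 = -3, then 0. SPID-12 = -6.5.
- Last score kept, 2 to 12 h: 10 × (-3) = -30. SPID-12 = -33.5.
- Difference: 27 point-hours.

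**A subject who improves.** Baseline 7, score 4 at 0.5, 1 and 2 h, then withdrawal. PIDs are 0, 3, 3, 3.

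- 0 to 2 h: 0.75 + 1.5 + 3 = 5.25.
- BOCF: 5.25 + 3 = 8.25.
- LOCF: 5.25 + 30 = 35.25.
- Difference: again 27.

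| Out after the 2 h score | BOCF | LOCF | Worse of baseline and last |
|---|---|---|---|
| Baseline 6, then 7, 8, 9 | -6.5 | -33.5 | -33.5 |
| Baseline 7, then 4, 4, 4 | 8.25 | 35.25 | 8.25 |

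**Range.** Measured against keeping the last score, the gain from BOCF is the rise in points times the weight of the missing part. That weight is 10.5, 9, 7, 5 or 3 hours for withdrawal after the 1, 2, 4, 6 or 8 h score. The gain runs from 1 × 3 = 3 to 5 × 10.5 = 52.5 point-hours.

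**Arm means.** One subject with a 27-point-hour gain moves a 30-subject arm by 27/30 = 0.9 and a 60-subject arm by 27/60 = 0.45. If the SD of SPID-12 were 20 to 25 (an assumption), 0.9 is about 0.04 SD. Two such subjects in a 30-subject arm give 54/30 = 1.8, or 0.07 to 0.09 SD. If 2% to 10% of an arm withdrew while worse, with gains of 6 to 22 each (also assumptions), the arm mean would shift by 0.02 × 6 = 0.12 to 0.10 × 22 = 2.2.

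**Does the per protocol analysis catch it?** Section 9.7.2.2 excludes subjects with 6 or more missing points in 12 h, or 3 or more in the first 6 h. A subject out after the 2 h score misses five (4, 6, 8, 10, 12 h), two of them in the first 6 h. Neither count excludes this subject, so the same imputed values can enter both analyses. The other evaluability criteria are not yet set (9.7.1.5).

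**The case against.** The best defence is that BOCF is a recognised, prespecified convention that gives no benefit after withdrawal. The body of the protocol is more specific than the synopsis, and 9.7 leaves further detail to a separate SAP. This is a single instillation with a 12-hour endpoint, so withdrawals may be few. Section 9.5.7 asks subjects who discontinue to complete the Visit 2 procedures where possible, and these include diary collection. Similar withdrawals in two arms would largely cancel. If they fall in the controls, BOCF works against URG101 and is cautious for the trial's claim. The worse-of-two rule is also a single imputation, with a bias of its own.

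Most of this stands as a limit on size and direction. It does not remove the conflict between the synopsis and 9.7.2.1, or the asymmetry of either rule.

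A reader might infer more than the documents support:

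- **That BOCF breaks a general principle of the plan.** Section 9.7.1.14 says "the most conservative PI scores (highest) will be used", but only for several scores recorded at the same date and time. It is a tie-break for duplicates.
- **That withdrawals with worse pain are to be expected.** Section 9.5.7 lists "AE(s), lost to follow-up, catheter intolerance, inadequate therapeutic effect, withdrawal of consent" among the reasons, but gives no rate. Catheter tolerance is assessed before dosing (9.1.2), so subjects who fail it without receiving drug are outside the ITT set.
- **That the subject is reset to no change overall.** On the natural reading only the later scores are replaced, and the example stays at -6.5. SPID-12 would be exactly 0 only if the rule were meant to replace every post-dose score.
- **That harm would go unseen.** Adverse events leading to discontinuation are listed separately (9.7.1.11).

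**Conclusion.** The point holds in a limited form. The synopsis and 9.7.2.1 prescribe different imputations for withdrawals on the primary endpoint, and this needs resolving whichever is preferred. Choosing one of the two does not settle the matter, because BOCF favours subjects who leave worse and LOCF favours those who leave improved.

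The size is 27 point-hours for the worked subject, or 0.9 on a 30-subject arm mean. Against planned effects of 0.60 and 0.75 SD this is probably small. That judgement rests on an assumed SD of 20 to 25 and on few such withdrawals, since the plan states neither figure. The gain from BOCF is measured against keeping the last score; had pain later fallen below baseline, BOCF would not flatter the subject. The direction of any between-arm bias cannot be told in advance. The change is worth making because it is cheap and removes an ambiguity in the primary analysis, not because the trial's conclusion is known to depend on it.

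**What to change.** State one rule in both the synopsis and 9.7.2.1:

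*For subjects who withdraw, each missing later score is imputed as the higher (worse) of the baseline score and the last observed score.*

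Limit the LOCF sentences in the synopsis and 9.7.2.2 to gaps in subjects who have not withdrawn. Keep plain BOCF as a named sensitivity analysis of SPID-12.

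The rule keeps the caution of BOCF for subjects who leave improved (8.25 in the example) and removes the unearned gain for those who leave worse (-33.5). It costs one sentence in each place and one line of code, and it leaves the planned sample size as it is. The downside is a slightly lower mean and a slightly larger variance of SPID-12 in arms with worsening withdrawals.
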